2.2. Secondary Objective

Increase lung function (FEV₁, FVC endpoints of 12% or more) and Improve FEV_1/FVC ratios.

3. Product Description

The product is a 20 mM (0.2%, 2.2 mg/mL) sodium pyruvate nasal spray in 0.9% sodium chloride with 0.02% benzalkonium chloride preservative, pH 7.2 (N115). The placebo control is 0.9% saline and 0.02% benzalkonium chloride preservative, pH 7.2. Both N115 and saline controls are delivered by a Mistette Mark II (MeadWestvaco, Richmond, VA, USA) nasal spray pump, or similar device, that delivers a 0.1 mL metered dose from a 30 mL polypropylene bottle. The product is sealed in tamper evident plastic and labeled with "Caution: New Drug—Limited by Federal (or United States) law to investigational use." 2 bottles are packaged in a white paperboard box with the expiration date of the product printed on the box. The N115 and placebo are packaged in identical packaging and are indistinguishable from each other to ensure blinding.

Good clinical practice (GCP) rules will be followed and the trial will be conducted, monitored, audited, recorded and the data reported to the Food and Drug Administration (FDA) and on clinicaltrials.gov.

4. **Qualifications of the Principal Investigator**

[name] [name] MD, the principal investigator for this study, is a board-certified physician who specializes in internal medicine. His research team has clinical interests in idiopathic pulmonary fibrosis, asthma and COPD. The references list shows the clinical studies in lung diseases in which [name] and his team have performed clinical research.

5.1. Pre-study

Individuals with a clinical diagnosis of idiopathic pulmonary fibrosis (as defined by the WHO and the Thoracic Society) will be solicited for participation in this phase 3 trial. After signing the informed consent, participants will be randomly assigned to either the placebo or drug groups in a double-blinded randomized fashion. On pre-study day 1 (Screening Visit), and, after signing the informed consent, they will have their degree of nasal inflammation and erythema, nasal cellular morphology, SaO₂, and FEV₁, and FVC levels recorded (baseline). All subjects will have a blood sample taken, and women of child-bearing age will provide a urine sample. The subjects will fill out a quality of life questionnaire (chronic respiratory disease questionnaire (CRDQ), and they will be given a data logbook in which they will record the number of coughs they experience each day for 7 days until they return to the clinic to begin the study (baseline). Any subject who is not compliant $\geq 80\%$ will not be entered into the trial.

Blood will be analyzed for CBCs, and for standard clinical variables, including urea nitrogen, serum creatinine, total protein, serum albumin, total globulin, albumin/globulin ratio, total bilirubin, alkaline phosphatase, aspartate aminotransferase (AST or SGOT), Alanine Aminotransferase (ALT or SGPT), Lactate Dehydrogenase (LDH), Gamma-glutamyl Transferase (GGT), Serum Sodium, Potassium, Chloride Serum, Carbon Dioxide, C-reactive protein, and Total Cholesterol:HDL Ratio to determine organ health. Subjects may not enter the study until the blood and urine samples are analyzed and evaluated to confirm that subjects do not have a metabolic abnormality that would prevent entry, and that women are not pregnant.

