5.2. Study Days

Following the 7-day pre-study period, which includes time for analysis of the blood and urine, eligible IPF patients will return to the clinic and be admitted to the 21-day study. On the first day of the study, these patients will have a physical exam and their vital signs will be recorded. Then, their degree of nasal inflammation and erythema will be evaluated and recorded as before, as will their SaO2, FEV1 and FVC levels and frequency of coughing. Patients will be instructed on how to self-administer their first dose of the nasal spray drug (0.2% sodium pyruvate in 0.9% sodium chloride solution) by first forcefully expelling air from their lungs, and

then spraying 3 squirts of the drug into each nostril, and then forcefully inhaling the drug so that the drug is inhaled into the lungs. After 1 hour, the subjects will have their vital signs taken again. Efficacy and safety evaluations will occur at this 1-hour time period, too, and then again at 2 and 3 hours. The subjects will fill out the product evaluation questionnaire, be given a daily data log form and be given enough drug to last for 21 days (3 bottles), and released from the clinic.

For the next 21 days, subjects will self-administer 3 squirts per nostril of the nasal spray, as instructed, 3 times daily; upon wakening, noon/midday, and before bedtime, Additionally, they will fill out the Daily Data Log form each day to record the number of daily coughs. Patients will be contacted by phone every 2 days to review symptoms and protocol compliance.

On days 8, 14 and 22, they will return to the clinic and have their blood analyzed, vital signs taken, and their degree of nasal inflammation, erythema and cellular morphology recorded. As before, they will be tested for FEV_1 , FVC and SaO_2 levels. The number of coughs they experienced and other information will be discussed with the clinician. They will fill out the product evaluation questionnaire and the CRDQ, and they will then be released from the study on day 22. These data will then be evaluated.

6. Criteria for Patient Selection, Exclusion of Patients, and Number of Patients 6.1. Subject Selection and Number of Patients to be Studied

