The patient population is adult patients \geq 40 years old with mild to moderate IPF with FVC and FEV1 values \geq 50% of predicted values. IPF is defined in accordance with the most recent collaborative guidelines from the American Thoracic Society, the European Respiratory Society, the Japanese Respiratory Society, and the Latin American Thoracic Association (56) including HRCT scan and/or lung biopsy consistent with unusual interstitial pneumonia (UIP), especially honeycombing, without identifiable cause related to other ILD such as drug toxicity, occupational or environmental exposure or connective tissue disease.

The study goal will be to enroll 25 patients with confirmed IPF into the trial in the sodium pyruvate (N115) treatment group and 25 with confirmed IPF to be enrolled in the trial in the placebo group. Efforts will be made to include women and minorities. The study will be a randomized, double-blinded placebo-controlled trial to subjects and study investigators.

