6.4. Inclusion of Women and Minorities

Every attempt will be made to include all genders and minorities that present with pulmonary fibrosis and are not exempted due to exclusion criteria.

7. Study Design

Assignment of Subject Number and Randomization

This is a randomized placebo-controlled double-blinded trial. Upon enrollment, each subject will be sequentially issued a unique subject number starting at 100. Once a number has been assigned to a subject, it cannot be re-assigned to another subject. Subjects will be encouraged to complete the study, although they may withdraw at any time without prejudice. Termination will be reported to the sponsor in a timely manner. Details of the reason(s) why a subject was dropped or withdrew from the study will be documented. Enrollment will continue until the number of subjects specified in the protocol has been attained. The data from all subjects that have been given a study compound will be retained for analysis.

8. Randomization

The subjects will be randomized to the placebo control or N115 drug study groups using a random number set.

9. Telephone Communication

Subjects will be instructed to call the clinic should they be experiencing any self-perceived adverse events, or if they have any study-related questions. All telephone information will be documented.

10. Products Description (How Administered)

The product is an all-natural patented 0.2% sodium pyruvate in 0.9% sodium chloride nasal spray solution, pH 7.2, with 0.02% benzalkonium chloride as a preservative. The patient will be instructed on the use of the nasal spray prior to the start of the clinical trial. The plastic bottle contains 30 mL. It is non-steroidal. Patients will forcibly expel air from their lungs and then will administer 3 sprays per nostril while inhaling strongly so that the drug is transported through the nose and into the lungs. The drug is to be administered 3 times per day (morning, mid-day, and evening). The product comes with instructions for administration (3 sprays per nostril).

11. Concomitant Therapy

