In the case of a subject lost to follow-up, attempts to contact the subject must be made and documented in the subject's medical records.

Withdrawn subjects will not be replaced.

15. A Description of Clinical Procedures, Laboratory Tests, or Other Measures to be Taken to Monitor the Effects of the Drug in Human Subjects and to Minimize Risk

Tests and analyses will be conducted 3 times during the study. If any aberrant values occur, the principal investigator will determine if that patient should continue in the study or be removed. All aberrant values that occur during the study will be considered adverse events. A summary of possible risks will be provided to the patients. Previous risks of using the product are minimal, which included irritation to the nose cavity reported by 1 patient out of 1,869.

16. Safety Precautions Included in this Study

The 0.2% nasal sodium pyruvate inhalation has been administered to both healthy humans and humans with lung diseases, without the occurrence of any SAE.

- First administration of nasal spray on the premises of a hospital/clinic.
- The initial nasal spray will be administered under the supervision of medical staff.
- If a subject develops any adverse event during the follow-up period after study drug administration, the subject will be treated to a satisfactory resolution before being discharged from the clinic.
- Subjects will remain at the test site for monitoring for 30 minutes after the initial inhalation of the nasal spray.
- Follow up telephone communications, as needed.

17. Product Evaluation Questionnaire

This self-administered questionnaire measures the patients' impressions of how the drug affected their nasal cavity, their coughing, and their breathing. It is designed to evaluate changes in a subject's quality of life over time. It will be administered during all clinic visits.

18. Daily Data Logbook

Subjects will use this diary card to record the number of their coughs per day, any self-perceived adverse events, and any medication changes during the study.

19. Urinalysis

Samples will be taken and analyzed to determine if any child-bearing females are pregnant.

20. Study Management

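### Section 5.1 places randomisation at consent, before the baseline diary and the entry checks, so some allocations can go to patients who never enter the trial

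*Combined protocol and SAP*

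**What the plan says.** Section 5.1 (Pre-study) introduces allocation directly after consent: "After signing the informed consent, participants will be randomly assigned to either the placebo or drug groups in a double-blinded randomized fashion". The same section then describes the screening measurements, a 7-day cough diary labelled as baseline, and two checks that can bar entry. A subject who falls short of 80% compliance "will not be entered into the trial". For the laboratory work, "Subjects may not enter the study until the blood and urine samples are analyzed and evaluated". Section 5.2 places entry after the 7 days: "eligible IPF patients will return to the clinic and be admitted to the 21-day study". The first dose is given at that Day 1 visit.

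Section 8 says only that a random number set will be used. It gives no timing, blocking or stratification. Section 7 issues the subject number on enrolment but does not time the allocation. The schedule in Section 13.1 has no row for randomisation.

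On numbers, Section 6.1 says: "The study goal will be to enroll 25 patients with confirmed IPF into the trial in the sodium pyruvate (N115) treatment group", with the same number for placebo. Section 7 continues enrolment until the specified number is reached and adds: "The data from all subjects that have been given a study compound will be retained for analysis". Section 14 says: "Withdrawn subjects will not be replaced". Section 20.2 treats a sample size of 20 as sufficient and chooses 25 per group to allow for non-completion and for incomplete or excluded data.

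**The concern.** A site that follows Section 5.1 allocates a patient about a week before it knows whether that patient may enter. Nothing is gained by this, because no study product is given until Day 1. Three things are at stake.

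- **Exclusions after randomisation.** Patients can be removed for diary compliance or laboratory findings after they hold an allocation. Both calls involve judgement: run-in compliance is not defined, and the metabolic abnormality that bars entry has no threshold. The plan does not say how a patient who is randomised but never dosed is counted, or whether that allocation is used again.
- **Arm sizes.** Even a balanced allocation list would not deliver equal arms at entry, because failures need not fall equally on the two arms.
- **Baseline after allocation.** Baseline is the covariate in the Section 20.2 analysis. The diary behind it is self-reported and would be filled in after assignment, so its integrity would depend wholly on concealment.

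**Working it through.** **1. Order of events.** Section 5.1: consent, random assignment, screening measurements, 7-day diary, 80% rule, laboratory review. Section 5.2: admission of eligible patients, pre-dose readings, first dose. Sections 7, 8 and 13.1 give no other time for allocation. So at least three steps that can bar entry (diary compliance, blood, urine) come after it.

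**2. The plan's own figure.** The 20 in Section 20.2 cannot be reproduced, because effect size, SD and power are not given. The text also does not say whether 20 is per group or in total. If it is per group, 25 corresponds to a 20% loss: 20 / (1 − 0.20) = 25. That rate is inferred, not stated. The stated purpose of the allowance is non-completion and unusable data, not failure before entry.

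**3. Where the 25 per arm is counted.**
- Section 6.1 counts patients enrolled into the trial. Section 5.1 uses matching language for those who pass the compliance rule.
- Section 6.3 puts the urine pregnancy test before enrolment, so enrolment is not consent.
- Section 7 keeps enrolling until the number is reached.
- The no-replacement rule in Section 14 is about subjects who withdraw.

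Together these support counting at entry.

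**4. Extra allocations on that reading.** Let f be the proportion failing before entry. The documents give no value, so the rates below are assumptions. Total to randomise = 50 / (1 − f), rounded up:

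| f | 50 / (1 − f) | Randomised | Allocations never used |
|---|---|---|---|
| 5% | 52.6 | 53 | 3 |
| 10% | 55.6 | 56 | 6 |
| 20% | 62.5 | 63 | 13 |
| 30% | 71.4 | 72 | 22 |

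**5. Balance at entry.** Two cases, since the method is only a random number set.
- *Simple randomisation.* Among 50 entrants, the chance of exactly 25:25 is C(50,25) / 2^50 = 11%, and the chance that either arm is below 20 is 12%. This is the same whether allocation is early or late, so it measures the method and not the timing.
- *A balanced list (hypothetical; none is described).* Randomising after the checks gives 25:25 with certainty. Randomising before them, with failures unrelated to arm, does not. With 28:28 allocated and 6 failing (10.7%), the chance of 25:25 is C(28,3)² / C(56,6) = 3,276² / 32,468,436 = 33%. With 32:32 and 14 failing (21.9%), C(32,7)² / C(64,14) = 24%. With 36:36 and 22 failing (30.6%), C(36,11)² / C(72,22) = 20%. The same hypergeometric sums put the chance of an arm below 20 at 0, 0.05% and 0.4%. The imbalance due to timing alone is therefore real but usually modest.

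**The case against.** The strongest reply is that consent fixes only an order, not a date. Section 7 carries randomisation in its heading and opens with what happens on enrolment, which Section 6.3 places after the urine test. Section 11 also bars intranasal products for a week before enrolment, which fits enrolment at the end of the pre-study week. On that view the sponsor already means to randomise at entry. This stands as evidence of possible intent. It does not settle the matter, because Section 7 times the subject number and not the allocation, while Section 5.1 is the only sentence that times the allocation.

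A second reply is that the order cannot bias the comparison. Packaging is identical, the trial is double-blind and no product is dispensed before Day 1, so pre-entry exclusions should not depend on arm. This stands if concealment holds. No route for a leak is described, though neither is a concealment procedure.

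A reader might go further and infer that 25 per arm shrinks before dosing. Assumed failure of 10%, 20% or 30% would leave 25 × 0.90, 0.80 or 0.70 = 22.5, 20 or 17.5 per arm. That needs the 25 to be counted at consent or randomisation with no top-up. Sections 6.1, 6.3 and 7 point the other way, Section 14 concerns withdrawals, and the failure rates are assumptions. Comparing those figures with a requirement of 20 per arm also assumes something Section 20.2 does not state. Nor does Section 7 say that only dosed subjects are analysed; it says that their data are kept.

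**Conclusion.** The point holds in a limited form. As written, allocation precedes the baseline diary and every entry check, and no other section corrects this. The consequences are avoidable exclusions after randomisation, unused allocations (about 6 to 22 for 50 entrants if 10% to 30% fail, both rates assumed), arm sizes at entry that even a balanced list would not control, and a baseline covariate collected after assignment. Erosion of the 25-per-arm target is not shown, and neither is bias. With concealment intact, the loss is in balance and efficiency. Moving randomisation would not by itself cure the chance imbalance of an unblocked random number set, which is a separate matter. This is a cheap improvement that should be made; it is not a demonstrated flaw in validity.

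**What to change.** - **Section 5.1:** delete random assignment at consent.
- **Sections 5.2 and 8:** state that randomisation takes place at the Day 1 visit, after the diary has been returned and has met the 80% rule, the blood and urine results have been reviewed, eligibility has been re-confirmed and the pre-dose readings have been recorded, immediately before the first dose.
- **Sections 6.1 and 7:** define enrolment as that point and count the 25 per arm from it.
- **Section 13.1:** add a randomisation row at Day 1, hour 0.

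The sample size need not change on this account. The cost is a few sentences and one schedule row, plus the small inconvenience that kits must be assigned at the Day 1 visit.

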The investigator is to record the use of all concomitant medications, both prescribed and over the counter (OTC) (including but not limited to natural food supplements), in the CRF. Subjects may continue to use their normal therapy as long as they list it as a current medication, and it is not prohibited by the exclusion criteria. Allowable concomitant therapy includes antiviral, antibiotic, antimicrobial, corticosteroids, antihistamines, or anti-inflammatory medications. The clinician may prescribe "rescue medication" should it be required by any of the patients. Patients may continue taking nutritional supplements as long as they do not contain pyruvate.

Subjects may not use any of the following during the trial or for 1 week before enrollment in the trial: all intranasal medications or lavages.

12. The Planned Maximum Dosage, and the Duration of Individual Patient Exposure to the Drug

This is a constant dose study. The amount of delivered sodium pyruvate was determined in prior clinical trials to be 3 sprays of 0.2% (2.2 mg/mL) sodium pyruvate in 0.9% sodium chloride solution per nostril, 3 times per day. The dose was determined by evaluating the data from both animal and human studies (cited above). Patients will forcibly expel air from their lungs and then will administer 3 sprays per nostril while inhaling strongly so that the drug is transported through the nose and into the lungs. The drug is to be administered 3 times per day (morning, mid-day, and evening). The product comes with instructions for administration (3 sprays per nostril).

13. A Description of the Observations and Measurements to be Made to Fulfill the Objectives of the Study

Observations for safety will include a pregnancy test for women of child-bearing age, blood tests for organ function, and vital signs. Adverse events will be monitored.

Observations for efficacy will include evaluation of lung function, as determined by FEV₁, FVC, nasal inflammation and erythema, and number of daily coughs.

13.1. Testing Schedule

Test	Screening	Day 1; 0,1,2,3 Hours	Day 8	Day 14	Day 22
Clinic Visit	+	+	+	+	+
Informed Consent	+				
Medical History	+				
Physical Exam/	+	+		+	+
Product Eval Q	+			+	+
CDRQ	+		+	+	+
Administer Drug		+	+	+	+
Blood Sample	+			+	+
Vital Signs	+	+	+	+	+
Pregnancy Test for Females	+				
Concurrent Medications Taken	+	+	+	+	+
SaO ₂	+	+	+	+	+
Nasal Inflammation	+	+	+	+	+
FEV ₁	+	+	+	+	+
FVC	+	+	+	+	+
Coughing Data Logbook*	+	+	+	+	+

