20.2. Data Collection, Management, and Statistical Analysis

The data management staff at the research clinic will collect and manage the data. Data will be obtained, maintained, and transmitted securely in accordance with HIPAA guidelines. Monitoring and auditing of the data will be conducted by a staff member of Cellular Sciences.

Statistical analysis will be performed on deidentified data. The basic statistical analysis will be repeated measurements of Analysis of Variance using baseline measurements as a covariant (ANCOVA). Age, sex, time since initial diagnosis with IPF, concurrent medications and smoking status are considered potential covariates. Number of coughing episodes reported for a 24-hour pre-study period, and other pre-study data information, will be compared to the data collected during the trial. The differences between baseline data and the data collected during the trial will be compared and analyzed (Within treatment). Additionally, the data of the patients on the experimental therapy will be compared to the data generated by the patients on placebo (Between treatments). P values of <0.5 will be considered significant. FEV1 and FVC will similarly be analyzed as secondary outcome measurements. Relative changes will be analyzed by JMP, Matillion, XLSTAT or R software by [name] or [name], who will be responsible for the statistical analysis.

Partial patient data will be included in the statistical analysis if patients withdraw from the study, but data from non-compliant patients will be excluded. Our previous research (REF) indicates that a sample size of 20 is sufficient to detect a statistically significant difference (p<0.05) between treatment groups. We have chosen to enroll 25 patients in each treatment group to ensure we achieve the necessary sample size, taking into account that some patients may not complete the study, and some data will be incomplete or excluded from the study.

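### Only the screening FEV1, FVC and SaO2 are labelled baseline; adjusting for the Day 1 pre-dose values as well would be a cheap gain in precision

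*Combined protocol and SAP*

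**What the plan says.** Section 5.1 has SaO2, FEV1 and FVC measured at the screening visit and tags that set as baseline: "FVC levels recorded (baseline". The next set comes at the first study day, "Following the 7-day pre-study period, which includes time for analysis of the blood and urine". Section 5.2 lists what is measured then, before the first self-administered spray: nasal findings are recorded, "as will their SaO2, FEV1 and FVC levels and frequency of coughing". The testing schedule in Section 13.1 agrees, with SaO2, FEV1 and FVC ticked under the column "Day 1; 0,1,2,3 Hours". Neither place calls the Day 1 hour-0 set baseline.

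Section 20.2 describes the model as "repeated measurements of Analysis of Variance using baseline measurements as a covariant (ANCOVA". It adds that "other pre-study data information, will be compared to the data collected during the trial", and that "FEV1 and FVC will similarly be analyzed as secondary outcome measurements". It does not say which visit supplies the covariate, or what happens when two pre-dose values exist.

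**The concern.** By its own labels, the plan adjusts spirometry for one reading taken about a week before dosing. A second pre-dose reading of the same quantities is collected anyway. A single reading carries measurement error and short-term variation that a second reading would partly remove. In a trial of 25 per arm, avoidable residual variance costs precision on FEV1 and FVC, which make up the whole secondary objective (Section 2.2). Leaving the visit unnamed also allows the covariate to be chosen after the data are seen.

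**Working it through.** **Inputs from the documents.** Two pre-dose sets about 7 days apart (Sections 5.1, 5.2, 13.1); post-treatment clinic visits on Days 8, 14 and 22 (Section 5.2); 25 per arm (Sections 6.1, 20.2); baseline-adjusted repeated-measures analysis (Section 20.2).

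**Input not in the documents.** The between-visit correlation r for FEV1, FVC or SaO2. I assume 0.5 to 0.95.

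**The plan's own figure.** Section 20.2 says 20 per arm suffices at p<0.05, but gives no effect size, SD or power, so the figure can be neither reproduced nor refuted. Back-solved at two-sided 0.05 and 80% power, it implies a difference of (1.960 + 0.842) × √(2/20) = 0.886 SD. It says nothing about residual variance after adjustment.

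**One post-treatment visit, equal variances, all correlations equal to r.** As a fraction of total variance, the residual is:

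- screening alone: 1 − r²
- mean of the two pre-dose values: 1 − 2r²/(1 + r)
- ratio of second to first: (1 + 2r)/(1 + r)²

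| r | Screening alone | Mean of two | Cut | 25 per arm acts like |
|---|---|---|---|---|
| 0.5 | 0.750 | 0.667 | 11.1% | 28.1 |
| 0.7 | 0.510 | 0.424 | 17.0% | 30.1 |
| 0.8 | 0.360 | 0.289 | 19.8% | 31.2 |
| 0.9 | 0.190 | 0.147 | 22.4% | 32.2 |
| 0.95 | 0.098 | 0.074 | 23.7% | 32.8 |

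The last column is 25/(1 − cut). As r approaches 1 the cut approaches 1 − 3/4 = 25%. A simulation at r = 0.8 (25 per arm, 5,000 runs) gave 19.5%. At r = 0.8, two-sided 0.05 and 80% power, the detectable difference falls from 2.802 × √(2/25) × √0.360 = 0.475 SD to 2.802 × √(2/25) × √0.289 = 0.426 SD.

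**Average of Days 8, 14 and 22, equal correlations.** The residual is (1 + 2r)/3 − r² with screening alone and (1 + 2r)/3 − 2r²/(1 + r) with the mean. At r = 0.8 that is 0.227 against 0.156, a cut of 31.4%. Over r = 0.5 to 0.95 the cut runs from 20% to 36%.

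**Correlation that decays with time.** With weekly correlation 0.7 to 0.95 and a measurement-error share of 0 to 10%, the cut is 4% to 16% at Day 22 and 14% to 28% for the three-visit average. The low end, at weekly correlation 0.7 and error share 10%:

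- screening with Day 22: 0.9 × 0.7⁴ = 0.216
- Day 1 with Day 22: 0.9 × 0.7³ = 0.309
- screening with Day 1: 0.9 × 0.7 = 0.63
- residual: 1 − 0.216² = 0.953 with screening alone, and 1 − (0.216 + 0.309)²/(2 × 1.63) = 0.915 with the mean, a cut of about 4%.

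**Direction.** Let s and d be the (non-negative) correlations of screening and Day 1 with the outcome, and c the correlation between the two. With equal variances the mean explains (s + d)²/[2(1 + c)]. If d ≥ s, this is at least 2s²/(1 + c), which is at least s². So the mean cannot do worse than screening alone under those conditions.

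**The case against.** Four objections deserve weight.

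**A reader might infer that the Day 1 value is discarded.** The documents do not say so. Section 20.2 names no visit, and its reference to pre-study data leans towards screening without settling the matter. The hour-0 reading also has an evident role as the reference for the 1-, 2- and 3-hour readings. What stands is narrower: no passage says that it enters the ANCOVA.

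**A reader might infer that the gain is a fifth.** That figure needs r near 0.8, equal correlations and one post-treatment visit. None of these is in the documents, and Section 20.2 plans a repeated-measures analysis.

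**The mean may not be the best choice.** Under decay with little measurement error, Day 1 alone does better: the mean's residual variance is up to 7% higher at Day 22 and up to 15% higher for the three-visit average. Two features of the plan could also make the readings less interchangeable. Section 11 bars intranasal products for a week before enrolment, and if enrolment means Day 1, screening readings may precede washout. The lung-function floor of 50% of predicted (Sections 6.1, 6.2), if judged at screening, truncates only the screening values. As an illustration with assumed correlations of 0.6 (screening–outcome), 0.8 (Day 1–outcome) and 0.6 (screening–Day 1), Day 1 alone leaves 1 − 0.64 = 0.360 and the mean leaves 1 − 1.4²/(2 × 1.6) = 0.388. This objection stands against the mean as a universal choice. Entering both values separately meets it: the residual is 1 − (0.36 + 0.64 − 2 × 0.6 × 0.8 × 0.6)/(1 − 0.36) = 0.338.

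**Randomisation appears to precede the Day 1 set** (Section 5.1). The reading is still taken before treatment under double blinding, so it remains a valid covariate.

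**Conclusion.** The point holds as a cheap improvement. The screening set is the only one labelled baseline, a second pre-dose set is already collected, and Section 20.2 does not bring it into the adjustment. Using both readings improves precision over screening alone in every case examined.

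The size is an assumption-based range: 17% to 22% for r = 0.7 to 0.9 within the wider 11% to 24%, with one visit and equal correlations; more for the three-visit average under equal correlations; as little as about 4% at Day 22 under decay. The documents support no single figure, and the range may differ between spirometry and SaO2.

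The scope is limited. FEV1 and FVC are secondary. SaO2 is measured, but it is named as an outcome neither in the objectives nor in Section 20.2. A reader might carry the gain over to cough, but that endpoint has its own diary baseline and is unaffected. Nothing here suggests bias in the treatment comparison.

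**What to change.** Add to Section 20.2, before unblinding, that the covariate adjustment for FEV1 and FVC (and SaO2, if analysed) uses both the screening value and the Day 1 hour-0 value, either as two separate covariates or as their mean. Choose one form in advance. Two covariates let the data weight the readings and guard against decay; the mean is simpler. Add that, if one value is missing, the available one is used (standing in for the other where two covariates are fitted).

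The change needs no extra visit, test or patient burden. Two covariates cost one degree of freedom: in a single-visit ANCOVA of 50 patients with intercept, treatment and baseline, residual degrees of freedom go from 47 to 46. The only other cost is writing the definition and the missing-value rule.
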